## 5. Statistical Analyses

### 5.1. General Considerations

- Efficacy endpoints will be listed using the mITT population.
- Safety endpoints will be listed using the Safety population.
- Partial dates will be treated as missing in computation or in variable derivation unless specified otherwise, but will be listed in the data listings as they appear on the eCRF.
- The baseline value as defined for the lead-in study will be used as the baseline in this extension study. For monthly endpoints, baseline is defined as assessments during the last 28 days of baseline period in the lead-in study. For efficacy and safety endpoints that are assessed at clinical visits, baseline is defined as the last non-missing efficacy or safety assessment, respectively, before the first dose of study intervention in the lead-in study.
- Study intervention is treatment administered (atogepant 60 mg QD).
- In general, statistical analyses will be performed using SAS version 9.4 or higher
- MedDRA version 24.0 or higher will be used to code adverse events, and medical history
- WHODrug Global B3 (v.202103 or higher) will be used to code medications.

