### 5.4.3. Adverse Events

Adverse events (AEs) will be coded using the Medical Dictionary for Regulatory Activities (MedDRA) version 22.1 or higher.

An AE will be considered as a treatment-emergent adverse event (TEAE) if the AE began or worsened (increased in severity or became serious) on or after the date of the first dose of double-blind study treatment in the lead-in study. An AE that occurs more than 30 days after the last dose of open-label study treatment or the safety follow-up visit (Visit 5) in this extension study whichever comes later will not be counted as a TEAE. Per case report form instructions, a new AE record will be created for any AE that worsens; therefore, TEAEs can be identified as those AEs captured in Study 3101-311-002 with recorded onset date on or after the date of the first dose of lead-in double-blind study treatment and within 30 days after the last dose of open-label study treatment or Visit 5 whichever comes later.

An AE will be considered as a treatment-emergent SAE (TESAE) if it is a TEAE that also meets SAE criteria.

TEAEs that started after the date of last dose of open-label study treatment will be considered as newly emergent TEAEs (NEAE).

Only TEAEs that started on or after the date of first dose of open-label study treatment will be summarized.

AEs will be listed on the Safety Population.

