### 5.4.4. Additional Safety Assessments

#### 5.4.4.1. Clinical Laboratory Parameters

Laboratory parameters in standard units at each assessment time point will be listed by study intervention group for the following laboratory parameters:

Category	Parameter
Chemistry	Sodium, potassium, chloride, bicarbonate, glucose, blood urea nitrogen, creatinine, total bilirubin, alkaline phosphatase, aspartate aminotransferase, alanine aminotransferase, lactate dehydrogenase, creatine kinase, total protein, albumin, calcium, phosphorus, uric acid, total cholesterol, the estimated glomerular filtration rate
Hematology	Hemoglobin, hematocrit, red blood cell count, red blood cell indices (mean corpuscular volume, mean corpuscular hemoglobin, mean corpuscular hemoglobin concentration), white blood cell count, including differential (neutrophils, lymphocytes, monocytes, eosinophils, and basophils), platelet count
Urinalysis	Specific gravity, pH

Clinical laboratory test values will be considered potentially clinically significant (PCS) if they meet either the lower-limit or higher-limit PCS criteria listed in Section 6.3.7.2. PCS laboratory values will be listed.

Participants with an adjudicated case (i.e. ALT  $\geq 3 \times$  ULN or AST  $\geq 3 \times$  ULN) will be listed with their ALT and AST assessments, adjudication dates, relationship of ALT or AST elevation to study intervention, and confounding factor(s). Additional listings will be provided for participants who meet ALT  $\geq 3 \times$  ULN or AST  $\geq 3 \times$  ULN and/or potential Hy's law and have one of the following categories: at least 1 abnormal liver biochemistry risk factor, at least 1 liver disease sign and symptom, at least 1 liver diagnostic test performed, consultation with a specialist for liver evaluation, liver lab tests performed, and drug screen performed, respectively.

Potential Hy's Law criteria within a 24-hour window is defined by a post baseline elevation of alanine aminotransferase (ALT) or aspartate aminotransferase (AST)  $\geq 3 \times$  ULN, along with total bilirubin (TBL)  $\geq 2 \times$  ULN and a non-elevated alkaline phosphatase (ALP)  $< 2 \times$  ULN, all based on blood draws collected within a 24-hour period.

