#### 5.4.4.3. Electrocardiogram

Listings for ECG parameters (ie, heart rate, PR interval, QRS interval, RR interval, QT interval, and QTc interval) at each assessment timepoint will be presented. The QTc will be calculated using both the Fridericia correction and the Bazett correction.

ECG parameter values are considered PCS if ECG values meet either the actual value or change from baseline PCS high criteria listed in [Table 6-5](#). Participants with PCS postbaseline values will be listed.

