## 6.2. Appendix 2: Changes to Protocol-Planned Analyses

The following changes to the Protocol amendment 1 were made in this SAP:

1. Section 7.2.2 of the protocol amendment 1 stated that “The related health outcome analyses will be documented in the health economics and outcomes research statistical analysis plan.” Instead, these health outcome analyses are added to this SAP document.
2. Removed following efficacy variables:
  - Change from baseline in monthly headache days at each monthly period.
  - Change from baseline in monthly acute medication use days at each monthly period.
  - $\geq 25\%$ ,  $\geq 50\%$ ,  $\geq 75\%$ , and 100% improvement (decrease) in monthly migraine days at each monthly period.
  - Change from baseline in monthly cumulative headache hours at each monthly period
  - Change from baseline in monthly triptan use days at each monthly period
  - Change from baseline in monthly moderate/severe headache days at each monthly period
  - Change from baseline in monthly severe headache days at each monthly period.
  - Other Health Outcome endpoints (see Section 5.3.1)
3. Efficacy variables will be listed, and will not be summarized.
4. Removed following demographic table summaries. Where noted in the body of the SAP, data will be presented in listings:
  - Analysis populations
  - Summary of enrollment category
  - Concomitant medication during the follow-up period
5. Removed following safety summaries. Where noted in the body of the SAP, data will be presented in listings:
  - TEAEs by SOC, PT and severity
  - NEAEs
  - Common ( $\geq 2\%$ ) TEAEs by PT
  - Summary of baseline, post-baseline, and change from baseline in laboratory parameters
  - Summary of baseline, post-baseline, and change from baseline in vital signs
  - Summary of baseline, post-baseline, and change from baseline in ECG

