**Table 6-9 Safety Analysis Visit Definitions**

Analysis Visit (Derived)	Scheduled Visit Day a	Window
Baseline		Baseline from lead-in study
Week 4	Day 28 (Visit 2)	Treatment Day [1, 42]
Week 8	Day 56 (Visit 3)	Treatment Day [43, 70]
Week 12	Day 84 (Visit 4)	Treatment Day $\geq 71$ and within the open-label treatment period
End of the Open-label treatment Period		Last available assessment during the open-label treatment period
Week 16 (Follow-up)	Day 112 (Visit 5)	Treatment Day [end of the open-label treatment period +1, the last study visit]
End of study		Last available assessment after treatment start date, i.e. occurs at final visit (expected Day 112) or ET

a Relative to the date of the first dose of open-label study intervention.

End of Treatment is defined as the last available assessment during open-label treatment period, i.e. on or before the treatment end date. End of Treatment results will be presented in summary tables for clinical laboratory values, electrocardiogram and vital signs.

End of Study is defined as the last available assessment during the study, including open-label and safety follow-up period.

End of Study results will be presented in summary tables for safety parameters, including but not limited to clinical laboratory values, and vital signs (not for electrocardiograms, as these data were not collected during follow-up period).

ET = early termination. EOS=end of study.

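### Does leftover summary-table wording in the SAP's data-handling appendix leave the safety outputs undefined?

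*SAP*

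**What the plan says.** The body of the SAP plans listings for safety data. Section 5.1 states "Safety endpoints will be listed using the Safety population". Section 5.4.4.1 says "Laboratory parameters in standard units at each assessment time point will be listed by study intervention group", section 5.4.4.2 lists vital signs, and section 5.4.4.3 announces "Listings for ECG parameters (ie, heart rate, PR interval, QRS interval, RR interval, QT interval, and QTc interval)" at each timepoint. Section 6.2 item 5, which records departures from the protocol's planned analyses, is headed "Removed following safety summaries. Where noted in the body of the SAP, data will be presented in listings". Its entries include "Summary of baseline, post-baseline, and change from baseline in laboratory parameters", the matching entries for vital signs and ECG, and three adverse event tables: by SOC, PT and severity; newly emergent events; and common events.

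Some text points the other way. The notes to Table 6-9 in section 6.4.1 say "End of Treatment results will be presented in summary tables for clinical laboratory values, electrocardiogram and vital signs" and then "End of Study results will be presented in summary tables for safety parameters, including but not limited to clinical laboratory values, and vital signs", with ECG excepted at End of Study. Section 5.4.3 says "Only TEAEs that started on or after the date of first dose of open-label study treatment will be summarized", and its next sentence says that adverse events will be listed. Sections 6.4.6 and 6.4.7 assign severe to a missing severity and yes to a missing causality when the event starts on or after the first open-label dose. Both send the imputed value to an incidence summary and show it as missing in the listings.

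**The concern.** Both instructions are current SAP text, so the conflict does not depend on comparing versions. Read literally, a programmer is told to list laboratory, vital sign and ECG results, to drop their summaries, and also to tabulate them at End of Treatment and, except for ECG, at End of Study.

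Adverse events look more serious, because safety is the primary objective. The rule for missing severity and causality is conservative by design, but it acts only through an incidence summary. If listings are the only output, the rule reaches nothing, and an event that would have counted as severe or related is shown with a blank. The restriction to events starting in the open-label period is also tied only to the word summarized, so the SAP does not say how the listing separates those events from ones dated back to the lead-in study. At stake is whether the safety report could differ according to which sentence is followed.

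**Working it through.** The SAP gives no figure to reproduce here. The check is a comparison of passages, with a little arithmetic on what the disputed tables could hold.

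**1. The passages side by side.**

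| Domain | Listing planned in | Summary removed in 6.2 item 5 | Leftover summary wording |
|---|---|---|---|
| Laboratory | 5.1, 5.4.4.1 | Yes | 6.4.1, End of Treatment and End of Study |
| Vital signs | 5.1, 5.4.4.2 | Yes | 6.4.1, End of Treatment and End of Study |
| ECG | 5.1, 5.4.4.3 | Yes | 6.4.1, End of Treatment only |
| Adverse events | 5.1, 5.4.3 | By SOC, PT and severity; newly emergent; common | 5.4.3, one sentence; 6.4.6; 6.4.7 |

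**2. Which text governs.** Section 6.2 item 5 addresses exactly these summaries and makes no exception for End of Treatment or End of Study. The 6.4.1 sentences sit in notes that define visit windows. Where the SAP means to keep counts, it says so: section 7 specifies the COVID-19 counts, and section 1 announces them. The consistent reading is listings throughout, with section 7 as the deliberate exception.

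**3. What a 6.4.1 table would add.** SAP section 3 expects about 3 participants. Protocol 7.3.1 names the statistics for continuous variables: n, mean, SD, median, minimum and maximum. Order three observed values as x1 ≤ x2 ≤ x3. Then:

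- minimum = x1, median = x2, maximum = x3;
- mean = (x1 + x2 + x3)/3;
- SD = √[Σ(xi − mean)²/2].

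Three of the statistics are the data themselves, and the mean and SD follow from them. SAP 6.4.4 puts all assessments in the listings and uses all post-baseline assessments for potentially clinically significant values. The table therefore holds nothing that the listing lacks, and leaving it out loses nothing.

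**4. What the imputation rules could change.** With 3 participants an incidence can only be 0/3 = 0%, 1/3 = 33.3%, 2/3 = 66.7% or 3/3 = 100%. Suppose one participant has one open-label event with missing severity, and nobody has another severe event. An incidence table using 6.4.6 gives 1/3 = 33.3% severe. The listing shows the same event with severity missing. These are two displays of one record, and a missing severity does not read as not severe. Protocol 6.1.1 requires the investigator to give severity, causality and start date for every event, so the case should be uncommon. Nor does the imputed value alter which events count as treatment-emergent: under 5.4.3 a worsened event gets a new record, and status is then set by onset date. The onset date set against the first open-label dose date also separates open-label events from earlier ones.

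**5. Remaining leftovers.** The count-once rule in 6.3.5, the summary-statistics clause in 6.4.4 and the coding rule in 6.4.10 are dormant if no table is made. Each of those sections also sends the data to listings. The drop from about 120 participants (protocol 7.5) to about 3 is stated openly in SAP section 3.

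**The case for a change.** The strongest case for a change is that a SAP should not give two incompatible instructions on the primary objective. Table and listing specifications sit in a separate document (SAP section 1). They may settle what is produced, but they cannot make the SAP itself consistent. The remedy would cost only a few sentences.

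Part of this stands. The 6.4.1 sentences do contradict 5.1, 5.4.4 and 6.2, and no summary by severity or causality is named anywhere for the imputed values to feed. The one adverse event table still named, COVID-19 events by preferred term in section 7, uses neither variable.

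The rest does not carry. It is too strong to say that the outputs cannot be determined, since 6.2 settles it for laboratory, vital sign and ECG data. It is also too strong to say that a causality table was withdrawn: none appears on the removal list. On imputation, two opposite remedies would serve equally well, either showing the imputed value beside the missing one or deleting both rules as unused. When opposite edits are equally acceptable, neither improves a number, its precision, its bias or participant safety.

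**Conclusion.** No change is called for. This is clerical residue: the main text and the appendix on departures were converted to listings, and some data-handling conventions were not. An analyst would follow sections 5 and 6.2, produce listings plus the section 7 counts, and leave the table-only rules idle. An analyst who produced the 6.4.1 tables as well would only restate listed values.

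The effect on results is nil. Every adverse event and every safety assessment is listed under either reading, SAP section 2 specifies no hypothesis, and the SAP plans no inference from an incidence out of 3.

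This rests on two assumptions. Enrolment must stay near the 3 expected; at the protocol's 120, listings would no longer convey what tables do, and the choice would matter. The separate output specifications, which are not available here, are taken to follow sections 5 and 6.2.

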## 6.4.2. Derived Efficacy Data

### 6.4.2.1. Derivation of Efficacy Endpoints Based on eDiary Data

For analysis purposes, four weeks (28 days) will be considered as one month. On a daily basis during the 4-week baseline period and throughout the open-label treatment period, participants are to record eDiary information on the duration of headache, headache specific characteristics and symptoms, the pain severity, and use of any acute headache pain medication. Daily headache diary data consists of data from “today’s diary” completed on that day and “yesterday’s diary” completed on the following day. Participants are to report headache data in “today’s diary” in the evening at any time from 19:00 to 23:59 and to complete “yesterday’s diary” on the following day to add the remaining headache data of previous evening until midnight. In case participants miss “today’s diary”, they can report the whole-day headache data in “yesterday’s diary” on the following day. In case participants miss “yesterday’s diary”, headache data from “today’s diary” alone will be used as daily headache diary data. If both “today’s diary” and “yesterday’s diary” are missing on one day, the daily headache diary data will be treated as missing.

Daily headache diary data will be merged from “today’s diary” and “yesterday’s diary” as following and will be used to derive migraine day and headache day.

- Daily headache total duration: summation of headache durations from “today’s diary” and “yesterday’s diary”
- Daily headache pain severity: the worst pain severity from “today’s diary” and “yesterday’s diary”
- Daily headache characteristics and symptoms: present if present in one of “today’s diary” and “yesterday’s diary”
- Daily acute headache medication usage: combination of acute headache medications usage from “today’s diary” and “yesterday’s diary”

If there are duplicate records of daily diary data for the same participant on the same day with the same type, the set of records with the last form access datetime will be used in the analysis.

The monthly migraine days is defined the total number of recorded migraine days in the eDiary divided by the total number of days with eDiary records during each monthly period and multiplied by 28. The baseline value as defined for the lead-in study will be used as the baseline in this extension study. For each postbaseline 4-week treatment period, a minimum of 14 days’ eDiary data during that period is required for the migraine days to be evaluable. If a participant does not have at least 14 days of diary data for a monthly treatment period, the migraine days for that period will be considered as missing. Migraine days will be derived for each participant at baseline and for each postbaseline monthly treatment period (Weeks 1-4, 5-8, 9-12). The same method to derive monthly migraine days will be used to derive monthly headache days, monthly acute medication use days, monthly triptan use days, monthly cumulative headache hours, monthly headache day pain intensity, monthly moderate/severe headache days, and monthly severe headache days.

If a subject reports ‘Yes’ to the intake of allowed medication(s) to treat an acute migraine but does not list any of them in the diary, then the acute medication use days will not be counted in this situation.

Subsequent to Day 1, the number of headache days will be counted in successive and non-overlapping 4-week (ie, 28-day) windows. Headaches that continue into a subsequent 4-week period will be counted (with recorded severity and duration) as occurring in each period.

If any postbaseline eDiary window for a participant has at least 14 but less than 28 days of reported data, the prorated approach will be used. If a participant reports less than 14 days of headache data, the participant's observed counts in that particular 28-day eDiary window will be set to missing for that window. These prorating rules will be applied to all efficacy analyses of eDiary data unless otherwise stated.

Monthly efficacy endpoints are defined in a prorated fashion. For example, monthly migraine days are defined as the total number of recorded migraine days in the eDiary divided by the total number of days with eDiary records during each monthly period and multiplied by 28.

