### 3. Sample Size Determination

Chinese participants who complete Study 3101-303-002, and meet all eligibility requirements, may participate in this extension study. Approximately 3 Chinese participants are expected to participate in this extension study. The sample size is different from the sample size planned in the protocol.

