**An acute medication use day** is defined as any day on which a participant reports, per eDiary, the intake of allowed medication(s) to treat an acute migraine. The allowed medications include the following categories of drugs: triptans, ergots, opioids, analgesics (including acetaminophen), NSAIDs (including aspirin), and antiemetics.

**A triptan use day** is defined as any day on which a participant reports intake of a triptan to treat a migraine per eDiary.

Headache day pain intensity is defined as the worst pain intensity on any headache day where headache pain intensity will be subjectively rated by the patient on a scale from mild to severe:

- Mild pain (=1)
- Moderate pain (=2)
- Severe pain (=3)

If participants experience no headache in a day, then the corresponding pain intensity of that day will be set as missing.

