#### Step 2: Calculate Monthly Scores and Baseline Score

Monthly scores will be calculated using the average daily scores only if there are at least 14 non-missing daily scores in the corresponding monthly (28-day) period. The corresponding monthly scores will be calculated by summing the non-missing daily domain scores and dividing by the number of non-missing daily scores, provided that 14 or more daily scores are available; otherwise it will be set to missing.

Monthly activity level score will be calculated by summing the non-missing daily scores and dividing by the number of these scores, provided that 14 or more daily scores are available in the corresponding monthly (28-day) period; otherwise it will be set to missing. Same rule will be applied to the calculation of monthly activity limitation score.

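### Does SAP 6.4.2.1 need correcting because it puts a 1-to-3 pain rating through a formula meant for counts?

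*SAP*

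**What the plan says.** SAP 6.4.2.1 builds monthly migraine days as the number of recorded migraine days "divided by the total number of days with eDiary records during each monthly period and multiplied by 28". It requires at least 14 diary days in the 28-day window. It then says seven other monthly variables are derived in the same way: headache days, acute medication use days, triptan use days, and "monthly cumulative headache hours, monthly headache day pain intensity, monthly moderate/severe headache days, and monthly severe headache days". It closes off exceptions: "These prorating rules will be applied to all efficacy analyses of eDiary data unless otherwise stated". No exception for pain intensity appears elsewhere.

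SAP 5.3.3 defines the daily quantity. On a headache day it is the worst pain rating, scored 1, 2 or 3. If there was no headache, "then the corresponding pain intensity of that day will be set as missing".

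SAP 6.4.3 treats a different daily rating differently: "Monthly activity level score will be calculated by summing the non-missing daily scores and dividing by the number of these scores", with no multiplication by 28.

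On use, SAP 5.3.1 names one derived endpoint for listing, the change in monthly migraine days, and says other efficacy measures collected will appear in listings. SAP 6.2 adds: "Efficacy variables will be listed, and will not be summarized". SAP Section 3 gives the scale of the study: "Approximately 3 Chinese participants are expected to participate in this extension study".

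**The concern.** Prorating to 28 days makes sense for anything that accumulates over days, such as a count of migraine days or a sum of headache hours. A severity rating does not accumulate. Six of the seven variables in the list are counts or sums of hours. Pain intensity is the odd one out.

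The SAP does not say what the numerator would be for a rating. The natural carry-over is the sum of the daily ratings. That sum grows with the number of headache days, so a participant whose headaches became rarer but no milder would appear to have lower intensity. The denominator also fits badly: ratings are missing on headache-free days, yet the formula divides by all diary days.

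If the variable were analysed, a fall in frequency could be read as a fall in severity, and a programmer following the text would output figures far outside 1 to 3 under an intensity label. The plain mean used for activity level suggests that the formula here was not a deliberate choice.

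**Working it through.** The documents give no worked figure for this variable, so there is nothing to reproduce. The check applies the SAP's rule to illustrative diaries.

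**Inputs.** Rating 1 to 3 on headache days, missing otherwise (SAP 5.3.3). Diary days D from 14 to 28 (SAP 6.4.2.1). H is the number of headache days and S the sum of the ratings, so S lies between H and 3H. The diaries below are invented for illustration.

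**Formulas.** Count: H ÷ D × 28. Same method applied to ratings: S ÷ D × 28. Comparator, the mean rating on headache days: S ÷ H.

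| Diary | Count | Ratings, same method | Mean rating |
|---|---|---|---|
| D = 28, 20 severe days | 20 | 60 ÷ 28 × 28 = 60 | 3.0 |
| D = 28, 10 severe days | 10 | 30 ÷ 28 × 28 = 30 | 3.0 |
| D = 28, 20 mild days | 20 | 20 ÷ 28 × 28 = 20 | 1.0 |
| D = 28, 10 moderate days | 10 | 20 ÷ 28 × 28 = 20 | 2.0 |
| D = 20, 10 moderate days | 14 | 20 ÷ 20 × 28 = 28 | 2.0 |
| D = 14, 10 moderate days | 20 | 20 ÷ 14 × 28 = 40 | 2.0 |

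The first two rows show the value halving at constant severity. The maximum is 28 × 3 = 84, a severe headache every day.

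**Does the result ever look like a rating?** Over all combinations of D from 14 to 28, H from 1 to D and S from H to 3H, there are 7,525 cases. In 38 of them the value falls between 1 and 3, always with 3 or fewer headache days. In only 3 does it equal the mean rating, each a single headache day in a full diary (for example 3 ÷ 28 × 28 = 3). So a value can land in the 1-to-3 range, but by coincidence. The quantity is a cumulative score.

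**Is information lost?** No. In every row, column three divided by column two gives the mean rating: 60 ÷ 20 = 3.0, 28 ÷ 14 = 2.0, 40 ÷ 20 = 2.0. The mean can also be taken directly from the daily ratings.

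**Where would the value be used?**

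- Protocol 7.2.1 includes moderate/severe and severe headache days, but not mean or monthly pain intensity.
- SAP 1.1 names only the change in monthly migraine days.
- SAP 6.2, item 2, removes headache days, acute medication use days, triptan use days, cumulative headache hours, moderate/severe headache days and severe headache days as efficacy variables. Those are all six companions of pain intensity in the list. Pain intensity is not named there, which is unsurprising, since that appendix records departures from the protocol and the protocol never had it.
- SAP 5.3.2 lists migraine days and nothing else.

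**Upper bound on the effect.** If the monthly value were listed after all: about 3 participants × 3 four-week periods = about 9 post-baseline values, with no summary statistic and no test.

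**The case for a change.** The strongest case for a change is that the text is explicit. The prorating rule covers all diary-based efficacy analyses with no carve-out, and the sentence on listing other measures collected could be read to include a monthly intensity. A programmer must then either print values of up to 84 as an intensity or depart from the SAP without a record. Reading the same-method sentence as meaning only the windows and the 14-day minimum does not rescue it, because the SAP would then have no formula at all for this variable. Deleting the phrase would cost almost nothing.

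The textual part of this stands: as written, the derivation does not yield a rating. The rest is conditional. The listing sentence speaks of measures collected, and what is collected is the daily rating, which is defined properly in SAP 5.3.3. No section calls for the monthly figure. Nor does the SAP require that a monthly intensity lie on the 1-to-3 scale. A cumulative 28-day score, placed next to cumulative headache hours, would be oddly named but computable.

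Two further arguments do not hold. Taking headache days as the denominator while keeping the 28 would give 28, 56 or 84 for uniformly mild, moderate or severe days, but the SAP nowhere states that formula. Re-deriving the baseline to match a new formula would collide with SAP 5.1: "The baseline value as defined for the lead-in study will be used as the baseline in this extension study". The lead-in definition is not in these documents, so a formula changed here could put baseline and follow-up on different scales.

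**Conclusion.** A clerical leftover, with nothing gained by amending the plan. The same-method sentence includes one variable that the formula does not suit, and applied to summed ratings it gives a frequency-driven score of up to 84. That variable is not an endpoint, its six list companions have been removed as efficacy variables, and no output is specified for it. The worst case is about 9 unsummarised values with a misleading label, from which the mean rating can still be recovered. Neither the safety objective nor the one listed efficacy endpoint depends on it. An analyst who needed a monthly intensity would average the rated headache days, in line with how SAP 6.4.3 handles activity level.

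This rests on two assumptions: that enrolment stays near the 3 participants stated in SAP Section 3, and that the separate document specifying tables and listings, which is not among those reviewed, does not call for the monthly value. If it does, the programmer should settle the definition there, after checking how the lead-in baseline was computed.
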